13.3. UNBLINDING

Safety or other clinical or legal considerations including requests from a child's family may, on rare occasions, require unblinding of the infant with regard to the actual intervention received. If such events make it necessary, the lab staff, responsible for preparation of study product at each site will be able to unmask the study drug product given to an individual infant. Before unblinding the lab staff must contact the Center's Investigator and the overall study Principal Investigators prior to releasing this information, and a protocol violation form will be completed.

13.4.INTERIM MONITORING FOR SAFETY OUTCOMES

The intervention for this trial will be conducted during the first 48 hours of life for the study subjects, while the primary outcome will be assessed at 12 (12 – 16) months of age. Thus, the primary focus of interim monitoring for this trial will be based on monitoring adverse events within 24 hours of cord blood infusion. Adverse events monitored will include the following, plus a composite (any of the listed events), on which statistical comparisons between the treatment groups will be based:

- Acidosis
- Allergic reaction/hypersensitivity
- GI Pathology
- Hemoglobinuria
- Hyperglycemia

A Phase II Multi-site Study of Autologous Cord Blood Cells for Hypoxic Ischemic Encephalopathy (HIE) IND 14753 (BABYBAC II)

- Hypoglycemia
- Hypertension
- Hypotension, and fever in the absence of neutropenia
- Hypoxia
- Infectious Disease
- Polycythemia
- Pulmonary Hypertension, within the first 24 hours
- Sinus bradycardia
- Sinus tachycardia
- Dyspnea
- Any other cardiac rhythm disturbances,
- Any other reported SAE, including death

In keeping with the Bayesian nature of the trial design, we will use a Bayesian interim monitoring approach to determine whether systematic differences are emergent among the two treatment groups in the incidence of any of the adverse events listed above. Specifically, after every 40 babies enrolled in the trial have spent 24 hours post their final study transfusion, we will calculate the posterior probability that one group has higher incidence of any adverse events than another. In statistical terms, the treatment will be considered harmful (i.e., the DSMC may consider termination of the trial) if for a pre-specified threshold η , the posterior probability of treatment harm (in terms of the above adverse events) is greater than η ; in other words if the predictive probability $P(\theta > 1 | X) > \eta$, where θ denotes the relative risk favoring the treatment group and X is the data available. In order to allow for a liberal safety monitoring regime to ensure patient safety, we propose to take $\eta = 80\%$. However, we will also present the 95% credible interval for θ , as well as the entire posterior distribution for θ in a graphical fashion to the DSMC so that they have a full appreciation for the range of possible values of θ . All interim analyses will adjust for baseline level of encephalopathy, the stratification variable for this trial, whenever computationally feasible.

The choice of a prior distribution is essential and controversial in Bayesian analyses. Thus, we can compute the posterior probability of treatment harm and the posterior distribution of the associated relative risk under two sets of priors – (a) a non-informative prior that does not assume any substantive prior information about treatment differences in terms of the adverse events listed above, and (b) an informative prior based on treatment differences for these adverse events observed in the Phase I trial. However, we realize that the standard Bayesian approach of running the analysis with different priors provides only a partial solution, as the results on stopping are often inconclusive, especially when few data have accumulated. Instead of worrying about the selection of a single correct prior, we will also explore the use of a robust Bayesian approach which replaces a prior distribution with a class of priors and calculates the corresponding posterior probabilities for decision making²⁶.

A Phase II Multi-site Study of Autologous Cord Blood Cells for Hypoxic Ischemic Encephalopathy (HIE) IND 14753 (BABYBAC II)

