11.4. SHORT TERM/HOSPITAL OUTCOMES/STUDY ENDPOINT

Short term outcomes will be considered secondary outcomes for the study. We will compare adverse outcomes, including mortality, seizures, need for nitric oxide and need for ECMO, need for G-tube feeding at discharge, and discharge on anti-epileptic medications. This information will be collected in case report forms.

11.5.LONG TERM OUTCOMES/PRIMARY OUTCOME/STUDY ENDPOINT

The Primary outcome of the study will be survival at one year with Bayley III scores in all three domains ≥ 85 .

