13.2. ADVERSE EVENT REPORTING

All adverse events reported or observed during the study beginning at the time of the autologous cord blood infusion must be recorded and maintained in the study participant’s paper files or electronic case report forms. Information to be reported includes when the site became aware of the event, investigator-specified assessment of severity and relationship to study therapy, whether there is an alternative etiology, seriousness, as well as any required treatment or evaluations, and outcome. In general, investigators should report adverse events as diseases or syndromes whenever possible, instead of reporting individual component symptoms, signs, laboratory abnormalities, and sequelae.

A Phase II Multi-site Study of Autologous Cord Blood Cells for Hypoxic Ischemic Encephalopathy (HIE) IND 14753 (BABYBAC II)

Severe adverse reactions (fatal or life threatening) that are unexpected and related will be reported to the FDA by Duke University within seven calendar days of receipt of the information by telephone, mail or fax, following FDA guidelines. All non-life threatening serious, related, and unexpected adverse events will be reported to the FDA via a written report within 15 days of receipt of the information (21 CFR 312.32) by Duke University. If the principal investigator assesses the event to be unrelated to the study, then the event will not require expedited reporting but will be included in a summary report.

Investigators are requested to notify the Principle Investigators at Duke University within 24 hours of all SAEs. The Principal Investigator or Sub-Investigator at each site is responsible for informing their Institutional Review Board (IRB). Copies of SAE correspondence with all Principal Investigators or Sub-Investigators, governing authorities, ethics committees, and the sponsor must be submitted to Duke University for filing.

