13.5. INTERIM MONITORING FOR EFFICACY OUTCOME

The relatively rare condition that this trial addresses means that it may take considerable time for this trial to enroll the requisite number of babies. Thus, even though the primary outcome is only available at 12 months corrected age, the enrollment period for the trial may make some interim efficacy data on the primary outcome available for monitoring by the DSMC. Note that because of the Bayesian nature of the trial design, interim efficacy looks at the data will not have any adverse Type I error consequences that are normally the case for a conventionally designed (or, ‘frequentist’) trial.

We propose to conduct one formal interim analysis of the accruing primary outcome data, examining both efficacy and futility, at a third of primary outcome accrual for this trial, provided that recruitment and intervention have not been completed by that point in time. The analysis for both efficacy and futility will adjust for baseline level of encephalopathy, the stratification variable for this trial, if computationally feasible

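### The interim rules in sections 13.4 to 13.7 disagree on which direction of the relative risk means benefit and on when futility is assessed

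*Combined protocol and SAP*

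**What the plan says.** **Section 13.4 (safety).** It states that "the primary focus of interim monitoring for this trial will be based on monitoring adverse events within 24 hours of cord blood infusion". It lists the events to be monitored, "plus a composite (any of the listed events), on which statistical comparisons between the treatment groups will be based", and the list ends with "Any other reported SAE, including death". After every 40 infants, the posterior probability of harm is compared with 80%. The parameter θ "denotes the relative risk favoring the treatment group", but the harm criterion is the probability that θ exceeds 1.

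**Section 13.5 (interim efficacy).** "We propose to conduct one formal interim analysis of the accruing primary outcome data". This covers both efficacy and futility, takes place once a third of the primary outcomes are in, and is done only if recruitment and intervention are still under way.

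**Section 13.6 (efficacy estimates).** RR estimates are announced for surviving without cognitive impairment. The same section describes harm as an RR above 1 and benefit as an RR below 1, and sets the skeptical, uninformative and enthusiastic priors at 1.1, 1.0 and 0.625. The DSMC may consider stopping for benefit if the upper 95% credible limit under the skeptical prior is below 1.0.

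**Section 13.7 (futility).** Benefit is a higher probability of that same favourable outcome with cord blood, glossed in a parenthesis as an RR above 1.0. The calculation is made at every safety look, projects to 120 infants with outcomes, and uses a 10% criterion.

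**Sections 15.2 and 15.3.** The sample-size text and the final analysis work with the adverse outcome: death or Bayley III below 85 in the first, a decrease in death or moderate/severe disability in the second. Unless the study ends early, the database locks after 160 infants.

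**The concern.** One set of priors and one fitted RR feed both the efficacy and the futility rule. If the RR is for a favourable outcome, values above 1 are good. If it is for an adverse outcome, values below 1 are good. Section 13.6 takes its outcome from the first convention and its thresholds from the second, and section 13.7 follows the first throughout. A programmer cannot implement the two sections together without choosing a convention, and the choice reverses what the DSMC would be told.

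On timing, the 10% futility criterion could be applied once or at every look, and the earliest looks come before the one-year assessments. Such a calculation would reflect mainly the prior, whose direction is itself in doubt.

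**Working it through.** **1. Reproducing 0.625.** Sections 5.2 and 15.2 give success (alive with all three Bayley III domains at 85 or above) in 16 of 25 cell recipients and 25 of 63 cooled-only infants.

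- Success, cooled-only over cells: 0.40/0.64 = 0.625 from the rounded rates, which is the plan's figure.
- Success, cells over cooled-only: (16/25)/(25/63) = 1.61.
- Adverse outcome, cells over cooled-only: (9/25)/(38/63) = 0.360/0.603 = 0.60.

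So 0.625 is a success ratio with the comparator in the numerator. It means benefit only on a scale where lower is better.

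**2. The sections side by side.**

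| Section | Outcome named | Benefit | Harm |
|---|---|---|---|
| 13.4 | Listed adverse events | Label says θ favours treatment | θ > 1 |
| 13.6 | Favourable | RR < 1 (0.625; upper limit < 1.0) | RR > 1 |
| 13.7 | Favourable | RR > 1.0 | not stated |
| 15.2, 15.3 | Adverse | decrease | not stated |

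Section 13.7 is consistent with its own outcome. Section 13.6 is not. In 13.4 only the label is off.

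**3. What the literal reading of 13.6 would do.** If the RR is success on cells over success on placebo, an upper limit below 1.0 means that cells do worse. As an illustration, take 27 infants per arm (a third of 160 is 53, or about 27 per arm), a vague prior approximated by log RR ± 1.96 SE, and assumed success rates. With 20% on cells and 40% on placebo, the rule signals benefit about 29% of the time. With 64% against 40%, it almost never does. The width of the skeptical prior is not given; a tight prior centred at 1.1 would lower the 29%. Conversely, on the scale of 13.7 a symmetric prior on log RR centred at 0.625 gives less than an even chance of benefit before any data, whatever its width.

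**4. Futility timing.** Inputs are 60–80 infants a year (section 6), looks every 40 infants (13.4) and a visit at 12–16 months (8.5.6). A look at N infants falls at month 12N/rate. Visits due = max(0, N − lag × rate/12).

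| Look | Month | Visits due, 60/year | Visits due, 80/year |
|---|---|---|---|
| 40 | 6–8 | 0 | 0 |
| 80 | 12–16 | 0–20 | 0 |
| 120 | 18–24 | 40–60 | 13–40 |

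For example, at 60 a year (5 a month) and a 12-month lag, the second look has 80 − 60 = 20 visits due. At the first look no Bayley result can be due. A death by then already settles that infant's outcome, but apart from such deaths the calculation rests on the prior.

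The single analysis in 13.5 comes later. A third of 160 (53 outcomes) is reached at months 20–27 and a third of 120 (40 outcomes) at months 18–24. By then 113–160 of 160, or 100–120 of 120, would be enrolled. With fast accrual, the proviso in 13.5 could therefore remove that analysis altogether.

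**5. 120 or 160.** The power table in 15.2 gives 0.92, 0.81, 0.62 and 0.38 for a control rate of 0.6 against 0.30, 0.35, 0.40 and 0.45. Exact enumeration of a 95% interval for log RR gives 0.924, 0.803, 0.612 and 0.393 at 60 per arm, and 0.971, 0.889, 0.715 and 0.470 at 80 per arm. The table and the projection in 13.7 therefore match 120 infants, while the lock in 15.3 is at 160.

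**The case against.** The fairest reply is that the intent can be recovered. Section 13.4 equates θ > 1 with harm in so many words. Section 13.6 says plainly that below 1 is beneficial and above 1 harmful. Section 13.7 says in words that success should be more frequent on cord blood. Sections 15.2 and 15.3 use the adverse outcome, and 15.3 uses the same three prior centres. A careful statistician would probably code the adverse outcome throughout. This stands as far as it goes: it makes the repair a matter of wording, and it means that one cannot infer that the trial would in fact be stopped in the wrong direction. It does not remove the conflict between the outcome named in 13.6 and its thresholds, or between 13.6 and 13.7. The rules are also advisory, since crossing one only lets the DSMC consider stopping.

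A reader might also infer from 13.4 that mortality escapes monitoring, because death appears only in the last item of a 24-hour list. The documents do not support that. Death is on the list, and the 24-hour window is called the primary focus, not the only one. The comparison is described as being "in the incidence of any of the adverse events listed above", which leaves room for an item-by-item reading. Section 13.2 adds that "Investigators are requested to notify the Principle Investigators at Duke University within 24 hours of all SAEs", and section 11.4 says of the hospital outcomes: "We will compare adverse outcomes, including mortality". Death is also part of the primary outcome used in 13.5 to 13.7. The DSMC works under a charter (section 14) that is not among the documents and may already provide mortality by arm. What remains is a question to ask.

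**Conclusion.** Both contradictions stand on the text alone.

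- **Direction.** Section 13.6 names a favourable outcome but uses adverse-outcome thresholds, and section 13.7 reverses the threshold. The Phase I effect is 1.61 on one scale and 0.60 on the other, and the plan's 0.625 is neither. This needs no assumption. The 29% illustration does: it rests on assumed success rates and a vague prior.
- **Futility timing.** The criterion applies once, at a third of outcomes, under 13.5, and at every safety look under 13.7, including a first look with no one-year visit due. The counts assume steady accrual at the projected rate, visits at 12–16 months and no losses.
- **Totals.** The projection to 120 and the lock at 160 also need to agree.

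The wider reading, that the safety rule leaves deaths unmonitored or that its 80% threshold is faulty for mortality, is not established. The text should be corrected before any interim analysis is programmed.

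**What to change.** 1. In 13.4, 13.6 and 13.7, define RR as the risk of the adverse outcome on cells divided by that on placebo: the listed adverse events in 13.4, and death or any Bayley III score below 85 in 13.6 and 13.7. RR below 1 is then benefit and RR above 1 harm everywhere. Drop the label of θ as favouring treatment, replace the favourable outcome named in 13.6, and rewrite the parenthesis in 13.7 to match.
2. State all three priors on that scale. For the enthusiastic prior, say whether 0.625 is kept as a chosen value or replaced by the Phase I adverse-outcome ratio of 0.60.
3. Reconcile 13.5 and 13.7 on when the 10% futility criterion applies, including what follows if the proviso in 13.5 removes the formal analysis. Reconcile the projection to 120 in 13.7 with the lock at 160 in 15.3.
4. Optional query: ask whether the DSMC charter provides all-cause mortality by arm at each 40-infant look.

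The cost is a short text amendment and matching changes to the interim programs. No new data, visits or infants are needed.

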8.4. INFUSIONS

For babies meeting entry criteria, the first dose of cells/placebo will be infused intravenously as soon as possible. Infants will be pretreated with hydrocortisone, 1 mg/kg IV 30-60 minutes prior to each infusion if the subject was not on hydrocortisone for clinical purposes. The placebo group is receiving hydrocortisone to minimize the risk of infusion-related and/or allergic reaction to the placebo - the same risk minimization as for the active stem cell recipients. Cells/placebo will be infused over 10-20 minutes, followed by a saline flush ($\leq 5.0\text{mL}$) to clear the intravascular line. The study allows up to two doses of cells or placebo if the cell number is adequate from the cord blood unit. There must be a minimum of 8 hours between doses and both doses need to be completed by 48 hours post delivery. Babies receiving placebo infusions will be treated in an identical fashion to those receiving cells. The infusion product will be blinded to the hospital staff administering the cells and evaluating the babies' outcomes, as well as the family.

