13.6. INTERIM ESTIMATION OF TREATMENT EFFICACY

This interim efficacy analysis will first evaluate whether the intervention is beneficial, equivalent, or harmful relative to usual care. A Bayesian logistic regression model will be fit to the data to obtain adjusted estimates of interim treatment efficacy, adjusting for the trial stratification variables.

A prior distribution is chosen in Bayesian analyses to provide an estimate of initial beliefs concerning the size of the potential treatment benefit. Thus, if one hopes that the results from the trial will influence the treatment of future patients, the prior distribution should represent the level of skepticism that is expressed by those clinicians that one seeks to influence. There are three principal types of prior we could use: (i) the uninformative, or reference prior, (ii) the skeptical prior and (iii) the enthusiastic prior. The uninformative prior represents a lack of clinical opinion as to the likely treatment difference, and in that sense contains no information about prior beliefs or other prior knowledge (eg. a relative risk for treatment benefit set at 1.0). A skeptical prior would be that overall effect of cord blood is actually harmful in this setting (i.e., a relative risk set higher than 1). An enthusiastic prior would be that the treatment is beneficial, as in the Phase I trial (relative risk set lower than 1).

It is generally useful to present the results of Bayesian analyses under several alternative prior distributions, so that the impact of differing levels of prior belief on the observed data may be reviewed. The uninformative prior has the advantage of corresponding roughly to the classical frequentist approach, and so this together with the skeptical and enthusiastic priors gives a broad and useful overview of the implications of terminating a clinical trial²⁷. Accordingly, we will use

A Phase II Multi-site Study of Autologous Cord Blood Cells for Hypoxic Ischemic Encephalopathy (HIE) IND 14753 (BABYBAC II)

all three prior distributions to present adjusted mean posterior relative risk (RR) estimates of treatment efficacy relative to survival free of cognitive impairment, along with corresponding 95% credible intervals for the same. These priors will be set at RR = 1.1 (skeptical prior), 1.0 (uninformative prior) and 0.625 (enthusiastic prior).

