The DSMC may consider proposing termination of the trial for benefit if the upper 95% credible limit for the mean posterior RR of treatment benefit, calculated using a skeptical prior, is less than 1.0. We propose to use a skeptical prior for this consideration to provide a more conservative basis for trial termination, and also to convince even those who strongly believed at the outset that the intervention will not succeed in improving survival free of cognitive impairment. In addition, we note that early stopping of a trial based on treatment benefit generally produces a biased and sometimes misleading estimate of the treatment effect^{28, 29}.

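### The harm trigger in section 13.4 is, on its plainest reading, weak for hospital deaths later than 24 hours after infusion, and the plan states no between-arm mortality comparison or threshold for them.

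*Combined protocol and SAP*

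**What the plan says.** Section 13.4 states that "the primary focus of interim monitoring for this trial will be based on monitoring adverse events within 24 hours of cord blood infusion". It lists the events, "plus a composite (any of the listed events), on which statistical comparisons between the treatment groups will be based". The last item is "Any other reported SAE, including death"; death has no line of its own. Looks take place "after every 40 babies enrolled in the trial have spent 24 hours post their final study transfusion", and the DSMC may consider stopping if the posterior probability of harm on these events exceeds 80%. Section 8.4 adds that "both doses need to be completed by 48 hours post delivery".

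Three other provisions bear on later deaths:

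- Section 13.5 sets one formal analysis of the primary outcome "at a third of primary outcome accrual for this trial, provided that recruitment and intervention have not been completed by that point in time". Section 13.6 says of it: "This interim efficacy analysis will first evaluate whether the intervention is beneficial, equivalent, or harmful relative to usual care". A numeric rule for benefit follows ("The DSMC may consider proposing termination of the trial for benefit if the upper 95% credible limit" falls below 1.0, under the skeptical prior). Section 13.7 gives one for futility. Neither section gives one for harm.
- Section 13.7 asks for a futility calculation at each safety look from the data then available, mainly under an optimistic prior, with a 10% threshold.
- Section 14 gives the DSMC a general safety remit under a charter, which is not among the documents.

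**The concern.** Death is part of the primary outcome and is common in this population. Section 5.2 reports that 11% of cooled infants without cells died before discharge, and section 5 cites 24-38% mortality among cooled infants in the hypothermia trials. Some of these deaths may come after the third day of life. If the harm trigger closes at about 72 hours, or if death is pooled with frequent events such as hypotension and hyperglycemia, an excess of deaths on cells could build up without moving the one statistic that has a harm threshold. The next analysis that mentions harm arrives when most infants have been treated, and may not take place.

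**Working it through.** **1. Window.** Dosing ends by 48 hours (8.4) and the monitored period is 24 hours after infusion (13.4): 48 + 24 = 72 hours of age at the latest.

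**2. Accrual.** Section 6 projects 60-80 infants a year. Two years give 2 × 60 = 120 to 2 × 80 = 160, which reproduces the 120-160 in section 15.2.

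**3. Enrollment at the one-third analysis.** Let r be accrual per year, f the time to outcome in years (12 or 16 months, section 8.5.6), and d the share of infants who die early and count as failures at once. With uniform accrual,

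enrolled = N/3 + (1 − d) × r × f, where N = 160 gives N/3 = 53.3.

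| d | 60/yr, 12 mo | 60/yr, 16 mo | 80/yr, 12 mo | 80/yr, 16 mo |
|---|---|---|---|---|
| 0 | 113 | 133 | 133 | 160 |
| 0.11 | 107 | 125 | 125 | 148 |
| 0.24 | 99 | 114 | 114 | 134 |
| 0.38 | 91 | 103 | 103 | 119 |

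For example, 53.3 + 0.89 × 60 × 1 = 106.7. In the 160 cell recruitment is over, so the proviso in 13.5 would cancel the analysis once dosing is complete. With the 120 infants named in 13.7 (N/3 = 40) and d = 0.11, the results are 93, 111, 111 and 120, the last with recruitment complete.

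**4. How well each rule sees an excess of deaths.** The plan gives no operating characteristics for the safety rule, so these inputs are assumptions: hospital mortality 11% on placebo (from section 5.2) against 11%, 16.5% or 22% on cells; looks at 40, 80 and 120 infants (20, 40 and 60 per arm); flat Beta(1,1) priors; no stratum adjustment; hospital status known at each look; 200,000 simulated trials. A trial is flagged if P(risk on cells > risk on placebo) exceeds the threshold at any look.

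For the composite, with o the probability of any other listed event, m hospital mortality and w the share of deaths inside the window,

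P(any event) = 1 − (1 − o)(1 − w × m).

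With o = 0.6 and w = 0.5, placebo has 1 − 0.4 × (1 − 0.055) = 0.622 and cells with doubled mortality have 1 − 0.4 × (1 − 0.11) = 0.644. A doubling of deaths appears as 2.2 percentage points. The runs used o = 0.4, 0.6 and 0.8, equal in both arms.

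| Rule | No difference | 11% vs 16.5% | 11% vs 22% |
|---|---|---|---|
| Composite, 80%, 10-50% of deaths in window | 32-35% | 33-41% | 33-47% |
| Composite, 80%, all hospital deaths pooled | as above | – | 43-60% |
| SAE/death item alone, 80%, 10-50% in window | 30-33% | – | 36-62% |
| SAE/death item alone, 80%, no time limit | 30-33% | – | 68-80% |
| Death only, 80% | 32% | 62% | 85% |
| Death only, 90% | 17% | 43% | 71% |
| Death only, 95% | 8.5% | 29% | 57% |

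The SAE/death rows take other SAEs at 5%, 10% or 20% in both arms.

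**5. Limit.** If cells also raise the other listed events by 10-20% in relative terms, the composite flags 52-99%. The weakness therefore concerns harm seen mainly as death.

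**The case against.** A reader might infer that deaths after the window reach no stated calculation until the one-third analysis. The documents do not support that. A death is a known primary-outcome failure (section 15.2), so the 13.7 calculation may count it at each safety look. At 11% mortality about 0.11 × 40 = 4.4, 0.11 × 80 = 8.8 and 0.11 × 120 = 13.2 deaths would be expected by the three looks. This stands, but that rule asks whether any benefit would be found, mainly under a prior set at the Phase I benefit, which makes stopping harder. The spread of that prior is not stated, so its sensitivity to excess deaths cannot be calculated, and the table above does not include it.

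The 24-hour limit on deaths is also not certain. It is called the primary focus, the death item carries no window, and the list is monitored with the composite as an addition, so a wider-window or item-by-item reading is open. On the most generous reading, item by item with no time limit, the existing rule flags 68-80% of doubled-mortality trials. That is about as many as a death-only rule at 90%, though with 30-33% false alarms instead of 17%. The text does not settle which reading applies. Pooling all hospital deaths in the composite gives only 43-60%, so widening the window alone is not enough.

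Finally, SAEs are notified to the lead investigators within 24 hours (13.2), and the DSMC charter may already provide death tables. Case-by-case notification is not a between-arm comparison; the charter could close the gap.

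**Conclusion.** The point holds in a limited form. The plan states no between-arm comparison of mortality for monitoring and no harm threshold for later hospital deaths. On the plainest reading of 13.4, the only numeric harm trigger hardly separates doubled hospital mortality (33-47% flagged) from no difference (32-35%). Death alone at 90% separates them clearly (71% against 17%). For 11% against 16.5% it flags 43%, against 33-41% for the composite, so the benefit there is mainly fewer false alarms.

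These figures rest on assumed event rates and flat priors. They also assume that hospital status is known at each look, which favors the death-only rule. Nothing in the documents shows that cells cause late deaths: Phase I recorded 0 of 39 before discharge, without randomization. Nor can it be concluded that the DSMC will be without mortality data. The change is worth making, with moderate confidence, because it is cheap and protects infants while most of the sample is being treated.

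**What to change.** Keep the 24-hour comparison for infusion reactions. In 13.4 add, at each 40-infant look, a separate between-arm Bayesian comparison of all deaths up to NICU discharge or data cut. Give it its own pre-specified advisory threshold, for example 90%, agreed between the sponsor and the DSMC. State whether the listed events are compared one by one and which window applies to each. If the charter already contains such a comparison, cite its section in 13.4.

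The cost is protocol wording and one more table per look. No new data are needed, because mortality and adverse events are already recorded (11.4, 13.2). The drawback is about 17% false alarms over three looks at 90%. At 95% this falls to about 8.5%, but detection of doubled mortality falls from 71% to 57%. These alarms come on top of those from the existing trigger, and the combined rate was not calculated. They are advisory, since the DSMC is not bound to stop.
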